5.2 Selection of Study Population

5.2.1 Inclusion Criteria

- 1. Signed and dated written Ethics Committee approved informed consent
- 2. Men aged 21 to 85 years with a histologic diagnosis of prostate cancer with a biochemical relapse following definitive local therapy (RP or radiation therapy)
- 3. Patients are not eligible or are unwilling to receive additional definitive therapy following relapse (either RP or radiation therapy)
- 4. No prior cytotoxic chemotherapy for the current cancer
- 5. Normal electrocardiogram (ECG) or ECG with no clinically significant findings as determined by the Principal Investigator
- 6. Presence of biochemically relapsed prostate cancer defined as either: 1) PSA > 2 ng/mL 1 year following initial definitive treatment for prostate cancer: or, 2) PSA doubling time (greater than 0.2 ng/mL) < 12 months; or, 3) PSA velocity > 2 ng/mL/year at any time following radical prostatectomy or radiation therapy.
- 7. Positive expression of HAAH in either archived tumor tissue (if available) or fresh serum
- 8. No clinical or radiologic evidence of distant metastatic disease as measured by pelvic MRI or CT scan in addition to bone scan. These studies will need to be performed within 56 (+ 7 days) days prior to the start of the study.
- 9. No history of immunosuppressive disease
- 10. No evidence of active autoimmune disease. Active autoimmune disease is defined as any disease process that has specifically needed administration of immune suppressive and or cytoreductive therapy currently or within the last 1 year.
- 11. Able and willing to comply with all study procedures

5.2.2 Exclusion Criteria

- 1. PSA doubling time of < 3 months
- 2. Participation in a clinical trial within 30 days prior to enrollment
- 3. Prior major surgery or radiation therapy within 4 weeks of enrollment
- 4. Any illness or condition that in the opinion of the Investigator may affect the safety of the patient or the evaluation of any study endpoint
- 5. Screening blood counts of the following: Hematopoietic:

Absolute neutrophil count $\leq 1500/\mu$ L,

```
Platelets \leq 100,000/\muL,
```

Hemoglobin \leq 9 g/dL;

Liver/Metabolic:

Alanine aminotransferase (ALT) and aspartate transaminase (AST) $\ge 2.5 \times ULN$ range, Total bilirubin $\ge 2 \times ULN$,

Albumin < 2.8 g/dL;

Renal:

Creatinine clearance \leq 50 mL/min as predicted by the Cockcroft-Gault formula

6. Subjects whose partners are WOCBP must use an adequate method of birth control while on study drug and at least for 3 weeks after discontinuation of study drug

- 7. Current or anticipated concomitant immunosuppressive therapy (excluding nonsystemic inhaled, topical skin and/or eye drop-containing corticosteroids)
- 8. Any concurrent condition requiring the continued use of systemic steroids (see above) or the use of immunosuppressive agents including methotrexate. All other systemic corticosteroids must be discontinued at least 4 weeks prior to first study treatment
- 9. Receipt of any blood product within 1 month of enrollment
- 10. Receipt of any vaccine within 4 weeks of enrollment
- 11. Active drug or alcohol use or dependence that, in the opinion of the Investigator, would interfere with adherence to study requirements
- 12. Been imprisoned or compulsorily detained (involuntarily incarcerated) for treatment of either a psychiatric or physical (i.e. infectious disease) illness
- 13. Patients who have a history of coagulopathies, thrombosis or who are receiving active anticoagulation for any condition, such as but not limited to, artificial heart valves, atrial fibrillation, etc.
- 14. Any other conditions judged by the Investigator that would limit the evaluation of a subject

5.2.3 Removal of Patients from Treatment or Assessment

The patients may withdraw from treatment with study product if they decide to do so, at any time and irrespective of the reason, or this may be the Investigator's decision to protect the safety of the patient. All efforts should be made to document the reason for discontinuation and this should be documented in the electronic case report form (eCRF).

Other criteria for possible discontinuation are:

- PSADT < 90 days
- Unacceptable toxicity as judged by the Principal Investigator

Adverse events which are dose-limiting toxicities

Patient is lost to follow-up

Patients will be followed up according to the study procedures as specified in this protocol up to the scheduled date of study completion, or up to recovery or stabilization of a followed-up AE, or the initiation of post study treatment, whichever comes last.

If possible, and after the permanent discontinuation of treatment, the patients will be assessed using the procedure normally planned for the 'end of study'.

The patients may withdraw from the study follow-up schedule, before study completion if they decide to do so, at any time and irrespective of the reason, or this may be the Investigator's decision:

Patients who are lost to follow-up:

- The Investigator should make every effort to re-contact the patient, to identify the reason why he/she failed to attend the visit, and to determine his/her health status, including at least his/her vital status. Attempts to contact such patients must be documented in the patient's records (e.g. times and dates of attempted telephone contact, receipt for sending a registered letter).
- Patients who did not complete the study and for whom no endpoint data are available will be considered as lost to follow-up.

The statistical analysis plan will specify how these patients lost to follow-up for their primary endpoints will be considered.

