| Dose cohorts will be enrolled sequentially and no dose escalation will occur until all patients in the current cohort complete the first 21-day cycle. After the first patient in each cohort has demonstrated adequate safety and tolerability for at least 21 days, the next 2 patients in the cohort may be enrolled. When at least 3 patients have reached Day 21 if none of the first 3 patients experiences a DLT, then dose-escalation to the next level can begin. Multiple patients can be in the screening phase but the first eligible patient able to be treated is assigned the treatment slot that is available for study. |
| A safety assessment of administration site reactions (ASR) will be made by the Investigator at least 30 minutes (or later) following each dose of study drug using the (NCI-CTCAE V4.03). Enrollment will be held if an ASR of grade 3 or greater (NCI-CTCAE V4.03) is observed, until the event resolves. In the event enrollment is held for an ASR, the Sponsor and Investigator will evaluate the outcome of the ASR and must agree to continued enrollment. |
| In patients who tolerate SNS-301, additional treatment may be continued with single doses of SNS-301 at their current dose level, to maintain geometric mean titer (GMT) of HAAH antibodies to no less than 4 times the baseline value for at least six months (9 injections). Treatment will be terminated with the 9th injection or will otherwise be terminated at any time upon the observance of PSA doubling < 90 days or occurrence of unacceptable toxicity. After termination, patients will be followed for an additional 6 months with monthly PSA levels and imaging studies as needed. If an unacceptable rise is detected in the patient's PSA levels following treatment discontinuation, patients shall be eligible for immediate resumption of therapy. |

Г

T

٦

| | Once the MTD/RP2D is determined, patients receiving ongoing treatment may be escalated to that dose for subsequent treatments. These patients will continue to be followed for safety and biochemical PSA monitoring. Pharmacodynamics: Exploratory pharmacodynamic (PD) analysis will be performed using dose, vaccine-specific antibody response (geometric mean of titer), antigen-specific T and B cell indices, and the relative expression of HAAH in each patient's tumor. The PD will be balanced and optimized to the degree of antigen-specific immune response and minimized for the production of |
|---------------------------------|--|

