5.2.4 Enrollment Holds

Enrollment will be held if the subject experiences a grade 3 or greater ASR as determined by the Investigator. The subject must be withdrawn from the study if they experience a grade 3 ASR. Enrollment can be re-started after agreement between the Principal Investigator, Medical Monitor, and the Sponsor.

Study enrollment will be halted in the event of a death of a subject while on the study or within a 30-day period follow study drug exposure regardless of drug relationship. In the event the enrollment is halted, a clinical review of the subject case will be made by the Principal Investigator, Medical Monitor, and the Sponsor to assess the safety of the medicinal product. If the review concludes there is no association of the death with the study drug, restarting enrollment may proceed.

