Treatment will be terminated with the 9th injection or will otherwise be terminated at any time upon the observance of PSA doubling < 90 days or occurrence of unacceptable toxicity. After termination, patients will be followed for an additional 6 months with monthly PSA levels and imaging studies as needed.

Once the MTD/RP2D is determined, patients receiving ongoing treatment may be escalated to that dose for subsequent treatments and receive a maximum of 9 injections. Patients who have received more than 9 injections due to the timing of the amendment limiting therapy to 6 months (9 doses), will be stopped at their last dose received and be followed for 6 months as with other patients. These subjects will continue to be followed for safety and biochemical PSA monitoring on a monthly basis for 6 months and are eligible to resume SNS-301 in case

of increases in PSA doubling to < 90 days or other evidence of disease progression and decline in immunological parameters.

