5.5.2.6 Additional treatment: Every additional 21 days ± 3 days if indicated

A maximum of 9 drug administrations will be administered on this study for all patients, except in the case of progression on study and or in the case of patients who had been on study for more than 6 months at the time of this amendment. Patients with evidence of progression and declining HAAH immune parameters within 6 months of stopping therapy have the option of resuming therapy on the study protocol.

- Immunologic blood collection pre-dose on day of drug administration every 21 days thereafter if continuing treatment.
- Symptom-directed physical examination
- Vital signs and ECG
- Eastern Cooperative Oncology Group (ECOG) performance score
- Prostate-specific antigen (PSA) assessment
- Biochemical testing: chemistry, hematology, coagulation, CH50
- Study treatment administration
- Physician administration site assessment (post-administration)
- Adverse events and concomitant medications

5.5.2.7 Follow up and End of Study (EOS): 28 days \pm 3 days after last treatment for a total of 6 months

- Complete physical examination
- Vital signs
- Eastern Cooperative Oncology Group (ECOG) performance score
- ECG
- Prostate-specific antigen (PSA) assessment
- Clinical laboratory tests, chemistry, hematology, coagulation, CH50 (only on first follow up)
- Immunologic blood collection
- Adverse events and concomitant medications

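### Resumption of SNS-301 does not exclude patients stopped for toxicity, grade 4 ASR is missing from the withdrawal sentence, and escalation has no explicit prior-DLT exclusion

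*Protocol*

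**What the plan says.** **Stopping for toxicity.** Protocol 5.3.5 says that treatment "will otherwise be terminated at any time upon the observance of PSA doubling < 90 days or occurrence of unacceptable toxicity"; the Synopsis and 5.1 carry the same rule, and 5.1 leaves the judgement to the investigator. Section 5.2.3 names "Adverse events which are dose-limiting toxicities" in a list headed "Other criteria for possible discontinuation are". Section 5.3.5.1 defines DLTs but states no consequence for the patient who has one. Section 5.3.5.2 deals only with related grade 2 events that are not DLTs.

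**Administration site reactions.** In 5.2.4 the hold reads "Enrollment will be held if the subject experiences a grade 3 or greater ASR as determined by the Investigator". The next sentence reads "The subject must be withdrawn from the study if they experience a grade 3 ASR".

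**Escalation of ongoing patients.** The Synopsis, 5.1 and 5.3.5 allow patients still on treatment to be raised to the MTD/RP2D once it is known. Additional treatment before that point is for patients who tolerate SNS-301.

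**Resumption.** The Synopsis, in the same paragraph as the termination rule, says that on an unacceptable PSA rise after discontinuation "patients shall be eligible for immediate resumption of therapy". Section 5.5.2.6 says that patients with progression and falling immune parameters within 6 months of stopping "have the option of resuming therapy on the study protocol". It also relaxes the dose cap: "A maximum of 9 drug administrations will be administered on this study for all patients, except in the case of progression on study". Table 1 note c and sections 3.4, 5.1 and 5.3.5 also offer resumption. SAP Section 4 repeats the termination, escalation and resumption text and adds no toxicity exclusion.

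**The concern.** In a dose-escalation trial, a patient taken off the vaccine for toxicity should not come back on through a rule that looks only at PSA, progression and immune markers. Followed literally, the Synopsis sentence permits this, because it applies after any termination and one of the three termination reasons is unacceptable toxicity. Such a patient would not be limited by the 9-injection cap either, since progression is an exception to it.

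The ASR wording has a similar defect: adjacent sentences use different thresholds, and the narrower one governs the patient. The escalation sentence matters because one DLT in six patients lets the next dose level open. A patient with a DLT may therefore still be on treatment when a dose 3 or 15 times higher becomes available.

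What is at stake is individual safety after cycle 1. The MTD rests on first-cycle DLT counts, which none of these sentences touches.

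**Working it through.** **Step 1: the provisions side by side.**

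| Provision | Where | What it depends on | Toxicity exclusion? |
|---|---|---|---|
| Resume after termination | Synopsis | PSA rise | None; toxicity is among the termination reasons |
| Resume | Table 1 note c, 3.4, 5.5.2.6 | Progression and falling immune parameters | None stated |
| Resume | 5.1, 5.3.5 | PSA doubling under 90 days or other progression, and immune decline | None stated |
| Withdraw for ASR | 5.2.4 | Grade 3 | Grade 4 not named |
| Escalate to MTD/RP2D | Synopsis, 5.1, 5.3.5 | Being on ongoing treatment | No explicit prior-DLT exclusion; the tolerability judgement comes earlier |

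Grade 4 is a category that the trial records: SAP 8.6.1 grades ASRs from 0 to 4. Under 5.3.5.1 a related grade 4 non-hematological event is a DLT of any duration. A related grade 3 ASR is a DLT only if it lasts more than 3 days despite supportive care. The milder event therefore has an explicit mandatory withdrawal and the more severe one does not.

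**Step 2: how often the escalation question could arise (illustration).** The plan's own figure reproduces: 3 levels × at most 6 patients = 18. The documents give no DLT rate, so p is assumed.

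Inputs from 5.3.5: a level opens the next after 0 of 3 DLTs, or after 1 of 3 followed by 0 of 3. The top level is cleared with at most 1 of 6.

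- a = (1−p)³ (0 of 3)
- b = 3p(1−p)⁵ (1 of 3, then 0 of 3)
- c = (1−p)⁶ + 6p(1−p)⁵ (top level cleared)
- 15-fold case, DLT patient at 2.0×10¹⁰: b(a+b)c, with 3.0×10¹¹ / 2.0×10¹⁰ = 15
- 3-fold case, DLT patient at 1.0×10¹¹: (a+b)bc, the same value when p is flat, with 3.0×10¹¹ / 1.0×10¹¹ = 3
- Either case: [(a+b)² − a²]c

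| Assumed p | b | a+b | c | 15-fold | Either |
|---|---|---|---|---|---|
| 5% | 0.1161 | 0.9734 | 0.9672 | 10.9% | 20.5% |
| 10% | 0.1771 | 0.9061 | 0.8857 | 14.2% | 25.7% |
| 20% | 0.1966 | 0.7086 | 0.6554 | 9.1% | 15.7% |

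A flat rate over a 15-fold dose range is generous to the concern. With assumed rates of 1%, 5% and 10% by level:

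- Level 1: a₁ = 0.9703, b₁ = 0.0285, sum 0.9988
- Level 2: a₂ = 0.8574, b₂ = 0.1161, sum 0.9734
- Level 3: c = 0.8857
- 15-fold: 0.0285 × 0.9734 × 0.8857 = 2.5%
- Either: (0.9988 × 0.9734 − 0.9703 × 0.8574) × 0.8857 = 12.4%

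If a DLT in the first (sentinel) patient closes the cohort at any level, the flat-rate 15-fold figures become (2b/3)(a + 2b/3)[(1−p)⁶ + 5p(1−p)⁵] = 6.7%, 8.3% and 5.0%.

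**Step 3: doses left at escalation.** With instant accrual and 21-day stages, a level-1 DLT gives 63 + 42 + 42 = day 147. A level-2 DLT gives 42 + 63 + 42, also day 147. A level-1 DLT patient first dosed on day 0 or 21 has had 7 or 6 injections by then, leaving 2 or 3 of 9. A level-2 DLT patient first dosed on day 42 or 63 has had 5 or 4, leaving 4 or 5. Real accrual leaves fewer. Resumption does not depend on this timeline.

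**The case against.** A reader might infer that no rule stops SNS-301 after a DLT and that a patient with a DLT can be escalated with no check on prior toxicity. The documents do not support that.

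- The heading in 5.2.3 is weak evidence that a DLT stop is optional. The same list contains PSA doubling time under 90 days and unacceptable toxicity, both mandatory stops under 5.3.5. If the DLT line is read as explaining the unacceptable-toxicity item just before it, the DLT stop is mandatory too.
- Escalation reaches only patients on ongoing treatment. They must have been judged to tolerate the vaccine, they can be terminated for unacceptable toxicity at any time, and escalation itself is permissive. The check exists; it rests on judgement and is not tied to DLTs.
- No text obliges anyone to resume or re-dose. Only the Synopsis sentence directly follows a termination that may have been for toxicity. In 5.1 and 5.3.5 the resumption text follows sentences on escalated patients and on those past nine injections.
- No sensible investigator would withdraw a patient for a grade 3 ASR and keep dosing after a grade 4, and termination for unacceptable toxicity would cover the grade 4 case.

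The first two points stand and limit what can be claimed about DLTs and escalation. The last two reduce the practical risk but do not repair the wording: resumption still lacks the exclusion wherever it is offered, and the two ASR sentences still disagree.

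**Conclusion.** The concern holds as a minor patient-safety wording gap. Its firmest parts are the Synopsis resumption sentence, which literally includes patients terminated for unacceptable toxicity, and the omission of grade 4 from the ASR withdrawal sentence. Both follow from the text alone. The missing prior-DLT exclusion for escalation is weaker, because a judgement of tolerability comes first. For DLTs other than a grade 3 ASR, stopping rests on investigator judgement, which is a design choice and not an error.

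The chance that a DLT patient from a lower level exists when 3.0×10¹¹ becomes the RP2D is about 16–26% for assumed flat rates of 5–20%, and about 12% for assumed rates of 1%, 5% and 10% by level. The 15-fold case alone is 9–14% and about 2.5%. It would be wrong to read these as chances of re-dosing: they assume nothing about whether the patient is still treated, and few injections may remain. The frequency of resumption after a toxicity stop cannot be estimated from the documents. Nor does the gap bias the MTD, since cycle-1 DLT counting is unchanged.

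**What to change.** 1. Wherever resumption is offered (Synopsis, Table 1 note c, 3.4, 5.1, 5.3.5, 5.5.2.6), add: *except patients who stopped for a DLT or unacceptable toxicity*. Leave the PSA-doubling stop and its option to resume as they are.
2. In the withdrawal sentence of 5.2.4, write *grade 3 or greater ASR*, matching the enrollment hold.
3. In the Synopsis, 5.1 and 5.3.5, limit escalation to ongoing patients *who have not had a DLT*.

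A mandatory permanent stop for every DLT is not needed to close these gaps. It would remove discretion even for a related grade 3 laboratory value that persists for more than a week. If the sponsor wants such a rule, it should be optional, with a defined exception for resolved laboratory-only DLTs.

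The cost is a wording amendment under 7.4, with written agreement and IRB notification, and no added patients, visits or procedures. The price to patients is that those stopped for toxicity lose the resumption option, and a patient with a prior DLT who continues stays at the original dose.

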5.2.4 Enrollment Holds

Enrollment will be held if the subject experiences a grade 3 or greater ASR as determined by the Investigator. The subject must be withdrawn from the study if they experience a grade 3 ASR. Enrollment can be re-started after agreement between the Principal Investigator, Medical Monitor, and the Sponsor.

Study enrollment will be halted in the event of a death of a subject while on the study or within a 30-day period follow study drug exposure regardless of drug relationship. In the event the enrollment is halted, a clinical review of the subject case will be made by the Principal Investigator, Medical Monitor, and the Sponsor to assess the safety of the medicinal product. If the review concludes there is no association of the death with the study drug, restarting enrollment may proceed.

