| | Treatment will consist of single repeated doses of SNS-301 administered every 21 days for 3 doses. A traditional 3+3 dose-escalation schema will be used to determine the MTD of SNS-301 for the first 2 doses and a modified dose-escalation schema for the remaining dose. Planned doses of SNS-301 are 2.0×10^{10} , 1.0×10^{11} and 3.0×10^{11} particles per administration diluted to 1 mL and administered intradermally. Additional patients will be enrolled at the highest dose level until at least 6 patients can be evaluated even if no DLTs are observed at the dose. Planned treatment may continue for two additional doses of SNS-301 administered every 21 days. Serum and whole blood samples will be obtained on the day of study treatment, at Day 1, Day 8, Day 15, and Day 22 during the first cycle. For patients who continue to receive study treatment, biochemical and immunologic testing will continue every 21 days. |
| | The MTD will be determined over the first 21-day interval following a single dose of SNS-301 in 3 dose cohorts. The MTD will be considered the dose level lower than the dose producing \geq 2 DLTs in 3-6 patients. Patients who withdraw in cycle 1 for reasons other than safety or toxicity will be replaced. Any of the following, if judged to be associated with SNS-301 |

| (i.e., possibly-, probably-, or definitely related to), will be considered a DLT using the National Cancer Institute-Common Terminology Criteria for Adverse Events (NCI-CTCAE) Version 4.03: |
|--|
| 1) Grade 4 non-hematological toxicities (excluding alopecia) of any duration |
| Grade 3 non-hematologic (non-laboratory) toxicity lasting > 3 days despite optimal supportive care |
| 3) Any Grade 3 or Grade 4 non-hematologic laboratory value if: a). Medical intervention is required to treat the patient; b), the abnormality leads to hospitalization; c). The abnormality persists for >1 week. |
| 4) Grade 4 hematologic toxicity, other than those specified in criteria 5 and 6 below, lasting > 7 days |
| 5) Grade 3 or Grade 4 febrile neutropenia of any duration |
| 6) Grade 3 thrombocytopenia in combination with a grade 3 or greater blood and lymphatic system disorder |
| 7) Grade 3 AST or ALT that is associated with a grade 2 rise in bilirubin |
| The recommended Phase 2 dose (RP2D) will be defined as the highest dose administered if no MTD is observed. |

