An evaluation period of at least 21-days for the first patient (sentinel patient) in a new cohort is required to evaluate tolerability before adding additional patients to the cohort. If safety/tolerability is adequate, then the remaining patients will be dosed in the cohort. A second evaluation will occur for the last patient of each cohort of at least 21-days to evaluate safety/tolerability before dose escalation to the next cohort will occur. Enrollment will be held if an administration site reaction (ASR) of grade 3 or greater (NCI-CTCAE V4.03) is observed until the event resolves. In the event enrollment is held for an ASR, the Sponsor, Medical Monitor and PI will evaluate the outcome of the ASR and must agree to continued enrollment.

Dose-escalation will proceed once all patients in a cohort (unless the MTD is observed) have completed a 21-day safety evaluation following the first dose of study treatment in the cohort. Planned treatment may continue for an additional 2 extra doses of SNS-301 administered every 21 days. Additional patients will be enrolled at the highest dose level until at least 6 patients can be evaluated even if no DLTs are observed at the dose. In patients who tolerate SNS-301, additional treatment may be continued with single doses of SNS-301 at their current dose level, to maintain geometric mean titer (GMT) of HAAH antibodies to no less than 4 times the baseline value for at least six months (9 injections). Treatment will be terminated with the 9th injection or will otherwise be terminated at any time upon the observance of PSA doubling < 90 days or occurrence of unacceptable toxicity as determined by the Investigator (either for that patient or in their dose cohort). After termination, patients will be followed for an additional 6 months with monthly PSA levels and imaging studies as needed.

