5.3.5 Selection and Timing of Dose for Each Patient

The MTD will be determined over the first 21-day interval following a single dose of SNS-301 in 3 dose cohorts. The MTD will be considered the dose level lower than that dose which produces \geq 2 DLT.

Dose-escalation will proceed when once all patients in a cohort (unless the MTD is observed) have completed a 21-day safety evaluation following the first dose of study treatment in the cohort. Multiple patients can be in screening phase simultaneously, but the first eligible patient able to be treated will be assigned the next treatment slot that is available for study.

More specifically, the first patient of each dose level will be enrolled and assessed for DLTs during cycle 1. Subsequent patients in a cohort can be enrolled after a 21-day review for tolerability by the Medical Monitor, Sponsor and Investigator(s) has been completed in the first patient.

After evaluation of the safety data of 3 patients in cycle 1 of the 2.0 x 10^{10} particles per administration dose, if none of the first 3 patients experiences a DLT, then dose-escalation to the next level (1.0 x 10^{11} particles per administration) can occur. When one patient shows a DLT, an additional 3 patients will be enrolled at the same dose level. If no more than 1 out of 6 patients experiences a DLT, patient enrollment to the next dose level can start.

Patients who withdraw from the study during cycle 1 (Day 1 - Day 22 pre-dose) for reasons other than safety or toxicity will be replaced.

Subsequent dose-escalation will be conducted in the same manner.

If the MTD is not achieved at the dose level of 3.0×10^{11} particles per administration, further dose-escalation will not be conducted. Additional patients will be enrolled at the highest dose level until at least 6 patients can be evaluated even if no DLTs are observed at the dose.

Although the dose-escalation process is guided by the safety evaluation during cycle 1, the global safety profile of SNS-301 at each dose level will be considered and discussed with the Investigator before increasing doses.

Planned treatment may continue for additional doses of SNS-301, administered every 21 days.

In patients who tolerate SNS-301, additional treatment may be continued with single doses of SNS-301 at their current dose level every 21 days, to maintain geometric mean titer (GMT) of HAAH antibodies to no less than 4 times the baseline value for at least six months (9 injections).

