5.3.5.1 Dose-limiting toxicities

Any of the following, if judged to be associated with SNS-301 (i.e., possibly-, probably-, or definitely related to), will be considered a DLT which are based on the NCI-CTCAE V4.03 criteria:

- 1) Grade 4 non-hematological toxicities (excluding alopecia) of any duration
- 2) Grade 3 non-hematologic (non-laboratory) toxicity lasting > 3 days despite optimal supportive care
- 3) Any Grade 3 or Grade 4 non-hematologic laboratory value if: a). Medical intervention is required to treat the subject; b), the abnormality leads to hospitalization; c). The abnormality persists for >1 week.
- Grade 4 hematologic toxicity, other than those specified in criteria 5 and 6 below, lasting > 7 days
- 5) Grade 3 or Grade 4 febrile neutropenia of any duration
- 6) Grade 3 thrombocytopenia in combination with a grade 3 or greater blood and lymphatic system disorder
- 7) Grade 3 AST or ALT that is associated with a grade 2 rise in bilirubin

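### Withdrawal from the study for a Grade 3 administration site reaction should read as stopping treatment, with follow-up kept and the patients who count for the MTD defined (minor)

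*Protocol*

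**What the plan says.** - **Withdrawal.** Protocol 5.2.4 holds enrollment for an ASR of Grade 3 or more and adds "The subject must be withdrawn from the study if they experience a grade 3 ASR". It sets no condition on duration. Enrollment restarts by agreement of the investigator, the medical monitor and the sponsor.
- **DLT status.** Under criterion 2 of Protocol 5.3.5.1 the event is a DLT only as "Grade 3 non-hematologic (non-laboratory) toxicity lasting > 3 days despite optimal supportive care". No other criterion captures a short Grade 3 ASR. A related Grade 4 ASR is a DLT at any duration.
- **Replacement.** Protocol 5.3.5 says cycle-1 withdrawals "for reasons other than safety or toxicity will be replaced". The synopsis agrees: "Patients who withdraw in cycle 1 for reasons other than safety or toxicity will be replaced".
- **Escalation.** Protocol 5.1 allows it "once all patients in a cohort (unless the MTD is observed) have completed a 21-day safety evaluation", and 5.3.5 repeats the condition. The synopsis adds: "When at least 3 patients have reached Day 21 if none of the first 3 patients experiences a DLT".
- **Follow-up.** Protocol 5.2.3 says "Patients will be followed up according to the study procedures as specified in this protocol", to study completion or recovery from the event, whichever is later. It adds that, if possible, "after the permanent discontinuation of treatment, the patients will be assessed using the procedure normally planned for" the end of study. It deals separately with withdrawal from treatment and withdrawal from the follow-up schedule.
- **Who counts for the MTD.** Protocol 5.2.3 leaves the handling of patients lost to follow-up for the primary endpoints to the SAP. SAP 6.3 places the primary endpoints outside its scope, and SAP 5 defines only a Safety and an Immunologic population.

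**The concern.** The event is serious enough to stop enrollment and remove the patient, yet it is not a DLT and gives no right to a replacement. If a site takes 5.2.4 at its word, 21-day safety data are lost on a man who has just had a Grade 3 reaction, and his cohort cannot meet the escalation condition as written. The gap is sharpest for the first patient in a cohort, because further enrollment waits on a 21-day review of that patient.

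The MTD rests on DLTs among 3 or 6 patients. Whether such a patient is still observed, and whether he counts, should be settled before the event occurs. The gap concerns cycle 1 only, since a reaction after a later dose does not enter the MTD.

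**Working it through.** **1. Planned size.** Three dose levels of at most 6 give 3 × 6 = 18, which matches the plan's figure of approximately 18. With no DLTs the number is 3 + 3 + 6 = 12.

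**2. One patient traced through the rules.** Take a patient at a lower dose with a related Grade 3 ASR lasting 2 days after dose 1.

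| Rule | Result |
|---|---|
| 5.3.5.1, criterion 2 | Not a DLT |
| 5.2.4 | Withdrawn from the study |
| 5.3.5 and synopsis, replacement | Not replaced, because the reason is toxicity |
| 5.1 and 5.3.5, escalation | All patients must complete 21 days; if he has left, he has not |
| 5.2.3 | Follow-up generally continues; end-of-study procedures if possible |

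If 5.2.3 governs, he completes the evaluation and stays in the denominator as a non-DLT. If 5.2.4 governs literally, the cohort has no stated way to finish. The synopsis wording of at least 3 patients might admit a fourth, but it neither says so nor lifts the all-patients condition. At the top dose enrollment continues until at least 6 can be evaluated, so this part of the gap is confined to the two lower doses.

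**3. The end-of-study visit alone.** Protocol 5.5.2.7 sets it 28 ± 3 days after the last treatment, so 25 to 31 days after a single dose. A laboratory DLT seen only at Day 8 or Day 15 and resolved by then would be missed unless those visits are kept. This is narrow: criterion 3 needs intervention, hospitalization or persistence beyond a week, and criterion 4 needs more than 7 days.

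**4. Illustration of size.** The documents give no DLT or Grade 3 ASR rate in patients, so every rate here is assumed. Let *p* be the true DLT rate and *q* the chance of a short cycle-1 Grade 3 ASR, independent of DLT. For one dose under the 3+3 rule:

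Pass(*p*) = (1−*p*)³ + 3*p*(1−*p*)⁵

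Suppose every such patient were lost and carried as a non-DLT. The observed rate becomes *p*(1−*q*). For *p* = 0.20 and *q* = 0.05 it is 0.19, and Pass = 0.81³ + 3 × 0.19 × 0.81⁵ = 0.5314 + 0.1987 = 0.730.

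| *q* | At least one in 3, 1−(1−*q*)³ | Pass, *p* = 0.20 (base 0.709) | Pass, *p* = 1/3 (base 0.428) |
|---|---|---|---|
| 1% | 3% | 0.713 (+0.4 points) | 0.434 (+0.6) |
| 2% | 6% | 0.717 (+0.9) | 0.441 (+1.3) |
| 5% | 14% | 0.730 (+2.2) | 0.461 (+3.3) |
| 10% | 27% | 0.752 (+4.3) | 0.494 (+6.6) |

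With follow-up kept, the observed rate is *p* and every shift is zero.

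**The case against.** The case on the other side is strong on consequences. The general follow-up sentence in 5.2.3 covers the study procedures, and those include Day 8, Day 15 and Day 22. Serious events are collected to 30 days after the last dose. The hold lasts until the reaction resolves and its outcome is reviewed, which requires the patient to be seen. All of this stands, and it makes loss of data unlikely.

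A reader might infer three stronger things that the documents do not support:

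- **That 5.2.4 contradicts 5.2.3.** It does not say whether it means leaving treatment or leaving follow-up. It is loosely worded, and 5.2.3 offers a reading under which the two agree.
- **That the plan would pass an unobserved patient as a non-DLT and so bias the MTD upward.** The escalation rule requires all patients in the cohort to complete 21 days, so the text blocks escalation in that case. The shifts tabulated above need that rule to be broken. Section 5.3.5 also has the overall safety profile considered before each increase.
- **That the DLT status of a short Grade 3 ASR is open.** The list in 5.3.5.1 is fixed in advance, and the event is not on it.

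It can also be objected that replacing incomplete toxicity withdrawals lets toxicity cases leave the denominator. That is a fair caution, and it is why follow-up must be secured first. As a bound, suppose every such patient were replaced, taking the ASR and a DLT as mutually exclusive. At *p* = 0.10 the rate among those counted is *p*/(1−*q*), and the pass probability falls from 0.906 to 0.897 at *q* = 5% and to 0.887 at *q* = 10%.

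What remains is that 5.2.4 is mandatory and literal, the replacement rule shuts out the patient it removes, and neither document says who counts for the MTD.

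**Conclusion.** The point holds as a minor correction. Taken literally, 5.2.4 gives a worse result than the rest of the protocol intends: it ends safety observation early in a patient with a Grade 3 reaction and leaves a lower-dose cohort without a rule for completion. The effect on the MTD is nil if 5.2.3 is followed. If 5.2.4 is followed and the escalation rule is kept, the result is a stalled or short cohort, not a wrong MTD.

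The event may well be uncommon: Protocol 3.2 reports no local reactogenicity in mice and rats, although the rat toxicology study found mild or moderate injection-site infiltrates that were non-adverse and resolved. The conclusion about wording rests on the text alone. The percentages rest on assumed rates and on a breach of the escalation rule, and should not be quoted as an expected bias.

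**What to change.** 1. **Protocol 5.2.4.** Say that a patient with a Grade 3 or greater ASR permanently discontinues study treatment, and that the Day 8, Day 15, Day 22 and end-of-study safety and laboratory assessments are kept. He then stays in the DLT denominator.
2. **Protocol 5.3.5 and synopsis.** Count for the MTD those patients who received dose 1 and either had a DLT or completed the 21-day evaluation. Replace a cycle-1 patient who meets neither condition, whatever the reason, and do not count him as a non-DLT.

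Whether a short Grade 3 ASR should itself be a DLT is a clinical choice for the sponsor; this fix does not require it.

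The cost is a few sentences in three places. With follow-up kept, replacement should rarely be needed. When it is, it takes one extra patient and about 21 days for that cohort, within approximately 18 unless all three cohorts have already reached 6. Some patients had passed 9 injections by the time of the amendment limiting treatment, so at least the first dose level has probably finished its DLT window. That is an inference; if it is right, the change mainly serves cohorts still in cycle 1.
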